#### **11.1.4 Expected side effects of Cisplatin and etoposide**

The side effects of cisplatin plus etoposide include, but are not limited to nausea, vomiting, decreased white blood cell count (more susceptible to infections), decreased red blood cells (or anemia, with risk of needing blood transfusion), decreased platelets (making it easier to bleed), fatigue, hair loss, hearing loss, kidney failure, sores in mouth leading to dysphagia, electrolyte abnormalities, neuropathy, fevers, chills, allergic reaction, confusion, difficulty with imbalance, cardiovascular event including heart failure, skin rash, liver failure.

### **11.2 Expected Acute Side Effects of Radiation Therapy**

Acute toxicity resulting from radiation therapy may include radioepithelitis of pharyngeal mucosa, xerostomia, thickened saliva, hypogeusia, dysphagia, hoarseness, nausea, emesis, skin irritation, erythema, epilation, weight loss, and fatigue.

### **11.3 Expected Late Side Effects of Radiation Therapy**

Late toxicity resulting from radiation therapy may include permanent xerostomia, hypogeusia, dysphagia, trismus, nasal dryness, serous otitis media, dental decay, esophageal constriction, permanent skin changes including telangiectasias, hypothyroidism, ototoxicity (especially if concurrent cisplatin is administered), and increased risk for secondary malignancies.

Osteoradionecrosis may occur in 5% or less of patients, but can be reduced by dental evaluation before radiation, as per the standard of care.

### **11.4 Toxicity Management**

Toxicities will be managed by the treating investigators according to best standard of care to ensure optimal supportive care of study participants.

### **11.5 Dose Modifications/ Delays**

At the discretion of the treating physician, any participant experiencing a grade 3 or higher toxicity may have a treatment break until resolution of the toxicity to grade 1 or less. If grade 3 toxicity persists, requiring a break of more than five consecutive treatments, the participant will be taken off protocol therapy per Section 13.0.

Cytopenias causing dose delays are not common with every three week dosing schedule and growth factors are not used in chemoradiotherapy protocols. Neutropenia of less than and ANC of 1000 and platelets of <100 would trigger a dose delay and re-assessment at 1 week. In the case of dose delays, the final dose of cisplatin may be given up to two weeks after completion of radiation therapy. Elevations in creatinine or BUN will be treated with extra sessions of intravenous hydration until the values normalize. Should the creatinine remain elevated between 1.4-1.6 mg/dl at the time of a subsequent dose, then cisplatin will either be dose reduced to 75 mg/m^2 or discontinued. The risks of permanent kidney damage with additional cisplatin will be discussed with the patient prior to further administration. For creatinine levels >1.6 further cisplatin will not be administered. Interruption of treatment may occur due to holidays, weather closing or machines are down.

## **11.6 Adverse Event Reporting**

This study will use the Common Terminology Criteria for Adverse Events (CTCAE) version v4.03 for adverse event (AE) reporting. After the Informed Consent Document (ICD) is signed, study site personnel will record the occurrence and nature of each patient's pre-existing conditions, including clinically significant signs and symptoms of the disease. During the study, site personnel will record any change in the pre-existing condition(s), and the occurrence and nature of any new adverse events.

Expected events during radiation therapy are:

- Fatigue/malaise
- Weakness
- Nausea
- Mild anorexia
- Oral mucositis
- Radiation dermatitis
- Xerostomia
- Dysphagia
- Tinnitus
- Dysgeusia

General Therapy Related Events:

- Catheter related events (thrombosis, bleeding, infection)
- Hospitalization for the management of any of the above expected events

Reporting Results:

- All AEs related to protocol procedures are reported. All AEs occurring after the patient receives the first dose of radiation therapy must be reported in regard to their assessment of the potential relatedness of each AE to protocol procedure, studied disease state, and/or radiation modality via CRF. If a patient's radiation treatment is discontinued as a result of an AE, personnel must clearly report the circumstances and data leading to any such dosage reduction or discontinuation of treatment.
- Events leading to the clinical outcome of death due to disease progression will be included as part of the safety and efficacy analyses for this study.
- If a death is considered related to treatment, the death should be reported as a Serious Adverse Event and appropriate guidelines followed for SAE reporting. Any clinically significant findings from labs, vital sign measurements, and other procedures should be reported as well.

## **11.7 Definitions of Adverse Events**

### **11.7.1 Adverse Event (AE)**

Defined as any harm or untoward medical occurrence in a research participant who is administered a medical product, medical treatment or procedure, even if it does not necessarily have a causal relationship with the product, treatment, or procedure. An adverse event can be any unfavorable and unintended sign (including an abnormal laboratory finding, for example), symptom, or disease temporally associated with the use of a medical product, medical treatment, or procedure, whether or not considered to be related. Resources containing information on AEs include monthly transcripts, assessment forms obtained after each clinic visit, and hospital progress and discharge notes. Grade  $\geq 3$  adverse events other than hematologic toxicities will be recorded, graded, and reported appropriately.

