#### **11.1.3 Expected side effects of Cisplatin**

The side effects of cisplatin include, but are not limited to, nausea, vomiting, decreased white blood count (more susceptible to infections), decreased red blood cells (or anemia, with a risk of needing a blood transfusion), decreased platelets (making it easier to bleed), fatigue, reversible hair loss, electrolyte abnormalities (e.g., hyponatremia, hypokalemia, hypomagnesemia), hearing loss, neuropathy, and kidney failure.

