### **11.8 Follow-up of Adverse Events**

All adverse events will be followed up according to Good Clinical Practice.

During Treatment: Throughout the duration of the study, site personnel will track any change in the condition(s), the occurrence, and the nature of any AEs, and record the highest grade of the adverse event per cycle on the CRF. CTCAE grading will be assigned before each visit for any adverse events experienced during the previous visit period.

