### **14.0 BIOSTATISTICS**

A one-stage design will be used for this trial. Of the 25 patients to be enrolled, 15 will be SCC patients and the remaining 10 will be ACC, Esthesio, or Adenocarcinoma. Based on historical data, current standard non-surgical treatment has a 1-year local failure rate of 40% for SCC patients and 65% for ACC, Esthesio or Adenocarcinoma patients. Therefore, a mixed cohort of 15 SCC and 10 ACC/Esthesio/Adenocarcinoma patients should have 1-year local failure rate of 50% under standard non-surgical treatment. We expect to decrease such a rate to 25% using the proposed new treatment. This design depends on a one-arm, one-sided binomial test and has a decision rule as follows: If, among the total 25 patients enrolled, we have at least 17 patients who are alive, followed and local failure free (or equivalently, at most 8 patients who are dead, lost to follow up or withdrew from the study, or have local failure) one year from the end of the treatment, then we shall declare the proposed treatment strategy

worthy of further investigation. Any patient who is taken off study due to unacceptable toxicities or lost to follow up, dies or withdraws within one year from the end of treatment will be regarded as a local failure. Patients who die during treatment will also be counted as failures, though such a probability will be small. This design has a type 1 error rate of 0.05 and type 2 error rate of 0.15 for testing the hypothesis  $p \geq 50\%$  vs  $p < 25\%$ , where  $p$  represents the 1-year local failure rate.

To assess the complications of minimally invasive endoscopic skull base surgery in patients with unresectable disease, we will use Clavien-Dindo classification of surgical complications and summarize the grades (I-V) and types. This will be done after surgery but before radiation.

To assess acute and long-term toxicity of radiotherapy, we will summarize the CTCAE v4.03 scores and present descriptive statistics. This will be done weekly throughout RT, at the end of RT, and then 3 months after the end of RT for acute toxicities. Long-term toxicities will be assessed at 6, 12 and 24 months after the end of RT.

Patient reported outcomes of toxicity due to radiotherapy, EORTC (H&N43 and QLQ C30) and SBI, will be summarized and reported at the following time points: After surgery (pre RT), week 4 of RT (+/- 7 days), 1 week within end of RT, and then at 3, 6, 12 and 24 months after the end of RT.

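### Section 11.7.1 names only grade 3 or higher non-haematologic adverse events for recording, while 11.6 and 11.8 cover all adverse events, so the data behind the CTCAE summary are not defined

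*Combined protocol and SAP*

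**What the plan says.** Section 11.7.1 first defines an adverse event broadly: "An adverse event can be any unfavorable and unintended sign (including an abnormal laboratory finding, for example), symptom, or disease". The definition has no grade floor and takes in laboratory abnormalities. The same section then ends by stating that grade 3 or higher "adverse events other than hematologic toxicities will be recorded, graded, and reported appropriately".

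Section 11.6 is wider. Staff are to record "the occurrence and nature of any new adverse events". It adds that "All AEs occurring after the patient receives the first dose of radiation therapy must be reported", through the CRF and with an assessment of relatedness. On laboratory results it says: "Any clinically significant findings from labs, vital sign measurements, and other procedures should be reported as well".

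Section 11.8 has CTCAE grades assigned before each visit for any event in the preceding period, and has staff "record the highest grade of the adverse event per cycle on the CRF".

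Section 14 sets out the analysis: "To assess acute and long-term toxicity of radiotherapy, we will summarize the CTCAE v4.03 scores and present descriptive statistics". The time points are weekly during radiotherapy, end of radiotherapy and 3 months for acute toxicity, and 6, 12 and 24 months for long-term toxicity. The Secondary Objectives in Section 2 contain one CTCAE objective for each period.

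Among the expected effects of cisplatin, 11.1.3 lists "decreased white blood count (more susceptible to infections), decreased red blood cells" and low platelets. Section 11.5 makes low neutrophil and platelet counts a reason to delay a dose.

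**The concern.** A descriptive toxicity table can only contain what was entered. If the closing sentence of 11.7.1 is taken as the recording rule, two groups of events drop out: everything at grade 1 or 2, and every haematologic event whatever its grade. The second group is one that the protocol itself expects with this chemotherapy and uses to decide whether the next dose goes ahead.

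The possible error runs in one direction. Section 3.6 hypothesises that the combined treatment will minimise toxicity. With a single arm there is no concurrent control whose data would be thinned in the same way, so under-recording would simply make the regimen look safer. It could also separate the safety result from the efficacy result: a patient removed for unacceptable toxicity counts as a failure under Section 14, yet if that toxicity were haematologic the adverse event table might not show it.

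**Working it through.** No sample size, error rate or event rate enters this point, so there is nothing to recompute. The check is a comparison of the recording rules.

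**Step 1. Scope of each rule**

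| Place | Grades covered | Haematologic events | Action |
|---|---|---|---|
| 11.7.1, definition | all | included (abnormal laboratory findings) | defines an AE |
| 11.7.1, last sentence | 3 or higher | excepted | record, grade, report |
| 11.6 | all | no exception; significant laboratory findings reported | record; report on CRF |
| 11.8 | all | no exception | grade before each visit; highest grade per cycle on CRF |
| 10.1 and 10.2, Tables 3 and 4 | all | no exception; Table 3 lists CBC and CMP with the weekly toxicity checks | CTCAE assessment weekly in radiotherapy, at its end, then at 3, 6, 12 and 24 months |
| 14 | all | no exception | summarise CTCAE v4.03 scores |
| 17.3 | by seriousness, not grade | no exception | SAE reporting |

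Only the last sentence of 11.7.1 is narrower than the rest, and it is narrower than the definition in its own section.

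**Step 2. What the difference does to single events.** Take four illustrative events during chemoradiation:

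| Event | 11.7.1 read as a limit | 11.6 with 11.8 |
|---|---|---|
| Grade 3 oral mucositis | recorded | recorded |
| Grade 2 oral mucositis | not recorded | recorded and graded |
| Grade 3 neutropenia that postpones a cisplatin dose, no admission | not recorded | recorded and graded |
| Grade 3 anaemia with an unplanned admission | not in the AE record, but an SAE under 17.3 | recorded and graded, and an SAE |

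The two readings agree on the first event and differ on the AE record for the other three.

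**Step 3. Could the sentence serve another purpose?** It might have been meant as a threshold for some form of reporting. Its verbs cover recording and grading as well as reporting, however, and it names no reporting route, so as written it cannot be confined to that purpose.

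**Step 4. Do low grades matter to this protocol?** Yes. Section 11.5 ties the end of a treatment break to resolution to grade 1 or less, and 11.6 lists a mild event (anorexia) among those expected. Both presuppose that grades below 3 are followed.

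**The case against.** The best defence is that 11.7.1 does not contain the word only. It says what will be recorded for one group of events and does not say that others will be left out. Read with 11.6, 11.8 and the assessment tables, the sentence is a stray emphasis, and staff would collect everything. A count low enough to delay a dose is hard to see as anything but a clinically significant laboratory finding, which 11.6 asks for. Serious haematologic events reach the SAE system under 17.3 in any case, and 11.5 remarks that cytopenias causing delays are uncommon on this schedule.

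Much of that stands. A reader might infer that the summary will omit all haematologic and all grade 1-2 events. The documents do not support this, because it requires 11.7.1 to override every other section and nothing says that it does. A reader might also picture different sites collecting different data. Section 4.2 describes a single-centre trial, so the risk lies in which section the staff of one centre follow.

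What the defence does not remove is the conflict itself. Under the harmless reading the sentence has no function, and no order of precedence is given. The requirement in 11.6 for significant laboratory findings is to report them; it does not settle whether they are graded and entered for the Section 14 table.

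It could also be said that Section 14 summarises toxicity of radiotherapy, to which cisplatin cytopenias do not belong. The objectives in Section 2 concern toxicity of treatment, which includes the chemotherapy.

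**Conclusion.** The protocol contradicts itself on which adverse events are recorded and graded, and the dataset for two secondary objectives is therefore undefined. Omission of haematologic and grade 1-2 events is a risk that materialises if staff follow the last sentence of 11.7.1; it is not a certain consequence of the plan.

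The size can be stated only in kind: one whole class of expected cisplatin toxicity, and all lower-grade events of any class. The documents give no incidence for either, so no count of lost events is offered. Serious events remain covered by 17.3. The primary endpoint and its decision rule are unaffected, since they rest on local failure, death, loss to follow-up, withdrawal and removal for toxicity.

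The conclusion assumes only that no CRF instruction outside these documents already settles the matter. It should be corrected because the correction is short and the possible error understates harm.

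**What to change.** Delete the last sentence of 11.7.1, or rewrite it to agree with 11.6 and 11.8: adverse events of all grades, including haematologic events from the scheduled CBC, are graded by CTCAE v4.03 and recorded on the CRF. State in Section 14 that the toxicity summary uses events recorded under that rule.

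If the grade 3 non-haematologic limit was meant for some other reporting purpose, say so explicitly at the place where it applies. It should not be placed so as to narrow 17.3: SAEs there are defined by seriousness, and a grade or organ-class limit could be read as exempting serious haematologic events.

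The cost is a short amendment and some extra CRF entry. CTCAE assessments and blood counts are already scheduled, so no visit or test is added and no treatment rule changes.

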### **11.7.2 Related or Possibly Related AE**

An AE is “related or possibly related to the research procedures” if, in the opinion of the principal investigator, it is more likely than not caused by the research procedures. AEs that are solely caused by an underlying disease, disorder, or condition of the subject, or by other circumstances unrelated to the research are not “related or possibly related”. If there is any question whether or not an AE is related or possibly related, Grade 3 or higher AE should be reported to the PI and IRB.

### **11.7.3 Unexpected AE**

An AE is “unexpected” when its nature (specificity), severity, or frequency are not consistent with (a) the foreseeable risk of adverse events associated with the research procedures described in protocol-related documents, such as the IRB-approved research protocol, informed consent document, product labeling and package inserts, and; (b) the characteristics of the subject population being studied, including the expected natural progression of any underlying disease, disorder or condition or any predisposing risk factor profile for the adverse event. AEs that do not meet the requirement for expedited reporting will be reported to the IRB as part of the annual renewal of the protocol.

### **11.7.4 Attribution to Therapy**

For reporting purposes, attribution is the assessment of the likelihood that an adverse event is caused by the research agent, or protocol intervention. The attribution is assigned by the principal investigator after considering the clinical information, the medical history of the subject, and the past experience with the research agent/intervention.

This is recorded using one of the following four categories:

- Related
- Possibly Related
- Not Related
- Unknown

“Related” events are those which are most certainly caused by the procedures involved in the research.

“Possibly related” events are those which may have been caused by the procedures involved in the research.

“Not related” events are those which are due to an underlying disease, disorder, or condition

of the subject, or due to other circumstances unrelated to the research or any underlying disease, disorder, or condition of the subject.

“Unknown” events are those which have an unclear relationship to the procedures involved in the research, either because more information is needed, and will be provided in follow-up, or because there is no way to make a determination.

### **11.8 Follow-up of Adverse Events**

All adverse events will be followed up according to Good Clinical Practice.

During Treatment: Throughout the duration of the study, site personnel will track any change in the condition(s), the occurrence, and the nature of any AEs, and record the highest grade of the adverse event per cycle on the CRF. CTCAE grading will be assigned before each visit for any adverse events experienced during the previous visit period.

## **12.0 CRITERIA FOR THERAPEUTIC RESPONSE/OUTCOME ASSESSMENT**

### **12.1 Local Failure**

The main cancer outcome of interest is local failure defined as recurrence of the primary paranasal sinus or nasal cavity cancer within the primary disease site at one year from end of treatment. Local responses to therapy will be recorded using RECIST 1.1 criteria with the baseline comparator MRI being the postoperative/pre-chemoradiotherapy MRI. Progressive disease (PD) per RECIST 1.1 will be defined as a local failure.

### **12.2 Locoregional Failure**

The cumulative incidence of locoregional failure will be recorded from the end of treatment. This will be defined as any progressive disease at the local site or regional/nodal (cervical/retropharyngeal) failure. If gross nodes are treated with radiotherapy, a regional/nodal failure will be defined using RECIST 1.1 as any progressive disease in a treated node. This will be assessed as per standard of care.

### **12.3 Distant Metastasis**

Distant metastasis is defined as any distant (below the clavicles) recurrence from the end of treatment.

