## **4.1 OVERVIEW OF STUDY DESIGN/INTERVENTION**

### **4.2 Design**

This is a single center, phase II, single-arm trial assessing the efficacy of local control of near-total endoscopic resection followed by proton-beam radiation with concurrent chemotherapy in unresectable paranasal sinus/nasal cavity tumors. The primary endpoint is local control at 1 year from the end of treatment with failure defined as progression of disease by > 20% of the 12 month post treatment MRI (per RECIST) compared to the post- surgical MRI. If a patient dies during treatment, he/she will be counted as a failure. We will secondarily assess regional/nodal failure and distant metastases, overall survival, disease specific mortality, and progression free survival. Treatment toxicity will be assessed by the Clavien-Dindo Classification of Surgical Complications and CTCAE v4.03 as well as PRO measures including EORTC HN and SBI. IMPACT testing will be performed for all patients undergoing treatment for this rare disease. Results of IMPACT testing will be banked for future investigation. We will include patients with a variety of histologic diagnoses including squamous cell carcinoma (SCC), esthesioneuroblastoma, adenoid cystic carcinoma, and adenocarcinoma. Patients will be included if there is multidisciplinary consensus that the primary lesion is not resectable with negative margin surgery without significant morbidity. This could include lesions that (1) involve the carotid artery, (2) invade brain parenchyma, (3) involve the orbital apex, (4) invade the pterygoid musculature, (5) involve the cavernous

sinus, (6) involve the clivus, and/or (7) involve intraconal space. Patients will only be included if there is multidisciplinary consensus that at least 80% of the tumor bulk can be removed without significant risk of morbidity. There is no cut-off for residual disease. Although expected that we will resect >80% of patient's tumor as discussed pre-operatively, if less than this is resected, patient will still proceed with protocol. Patients will be stratified by the pathologic diagnosis.

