### **9.2.2 Definition of Target Volumes and Margins**

GTV Gross Primary will include all existing gross disease at the primary site as seen on postoperative MRI and simulation CT scan. The CTV Primary Site will include the preoperative gross extent of primary tumor visible by imaging studies (CT, PET, and/or MRI), and/or clinical examination along with the postoperative surgical bed; for histologies with high risk of neutropic spread, a CTV Nerve will be created to encompass the affected nerve tracks. Fusion of preoperative and postoperative MRI to the simulation CT should be performed to aide in volume delineation. Irradiation of cervical and retropharyngeal nodal basins will be left up to the treating radiation oncologist. For patients in whom the cervical and retropharyngeal nodes will be treated, the CTV Node High Risk volume will include nodal basins wherein gross nodal was resected; CTV Node Low Risk will include nodal basins in which there was no gross nodal disease identified. If there are suspected grossly involved lymph nodes, a volume GTV Gross Node should be created. Skin bolus is acceptable and can be used for patients who are at high risk for skin involvement, at the discretion of the treating physician. Each CTV will be expanded by 3mm to a planning target volume (PTV), to account for intra-fractional patient motion, and inter-fractional setup error. The above are all standard radiation oncology treatment planning procedures.

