### **12.4 Progression**

Progression is defined from the end of treatment to first local, regional/nodal or distant recurrence event, or death.

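### Recurrence sites in Sections 12.1 to 12.4 are not exhaustive: a separate non-nodal recurrence above the clavicles is neither a distant nor a progression event

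*Combined protocol and SAP*

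**What the plan says.** Section 12 sorts recurrence by site.

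- **Local (12.1):** "recurrence of the primary paranasal sinus or nasal cavity cancer within the primary disease site at one year from end of treatment". No anatomical boundary is given. The section then adds: "Progressive disease (PD) per RECIST 1.1 will be defined as a local failure". It does not say whether a new lesion away from the primary site counts. Section 4.2 words the same endpoint as "failure defined as progression of disease by > 20% of the 12 month post treatment MRI (per RECIST) compared to the post- surgical MRI".
- **Locoregional (12.2):** "any progressive disease at the local site or regional/nodal (cervical/retropharyngeal) failure". Where gross nodes have been irradiated, "a regional/nodal failure will be defined using RECIST 1.1 as any progressive disease in a treated node".
- **Distant (12.3):** "Distant metastasis is defined as any distant (below the clavicles) recurrence from the end of treatment".
- **Progression (12.4):** time from the end of treatment to "first local, regional/nodal or distant recurrence event, or death".

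Section 14.0 adds no site definitions. It analyses progression-free survival by Kaplan-Meier, and regional and distant progression by cumulative incidence, with death without the event as a competing risk. Both are secondary objectives in Section 2.1.

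**The concern.** A set of failure sites used to build a progression endpoint should place every recurrence somewhere. This set leaves out disease that is above the clavicles, not in a node and not at the primary site.

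That region matters in this cohort. Sections 4.2 and 6.2 admit tumours that involve brain, cavernous sinus, orbital apex or clivus. Section 9.2.2 foresees spread along nerves: for some histologies "a CTV Nerve will be created to encompass the affected nerve tracks", as a volume separate from the primary-site volume.

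At stake are the secondary results on progression-free survival and distant metastasis. A patient with a new, separate intracranial deposit would be reported as free of progression and free of distant metastasis. In a single-arm trial no control group carries the same omission.

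**Working it through.** The plan states no figure on this point, so the check is to run plausible recurrences through the four definitions as written.

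| Recurrence | Local (12.1) | Regional (12.2) | Distant (12.3) | Progression (12.4) |
|---|---|---|---|---|
| Regrowth in the tumour bed | yes | no | no | yes |
| New neck node, no nodes irradiated | no | yes | no | yes |
| Lung lesion | no | no | yes | yes |
| Spinal leptomeningeal disease below clavicle level | no | no | yes | yes |
| Separate brain or dural deposit | no | no | no | **no** |
| Cranial leptomeningeal disease | no | no | no | **no** |
| Non-contiguous skull lesion | no | no | no | **no** |
| Extension contiguous with the bed, or along a nerve | unclear | no | no | unclear |
| New node elsewhere after gross nodes were irradiated | no | unclear | no | unclear |

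Three rows have no category. No other section supplies one.

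**Effect on progression-free survival.** For those three rows the event time becomes the date of death or of a later classified event. If neither occurs, the patient is censored without an event. For example, an unclassified recurrence at 6 months followed by death at 18 months leaves the patient progression-free at 1 year.

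**Effect on distant-metastasis incidence.** The patient never enters as an event on account of that recurrence. If the patient then dies, the death enters as a competing death without distant metastasis.

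**Size.** With n = 25 (Section 14.0), one missed patient moves a crude rate by 1/25 = 0.04, or 4 percentage points, and two by 2/25 = 0.08, or 8 points. The documents give no frequency for these recurrences, so no expected bias can be calculated. Its direction is favourable for both endpoints.

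**Primary endpoint.** Section 14.0 tests p, the 1-year *local* failure rate. Its 50% reference is also a local failure rate: (15 × 0.40 + 10 × 0.65)/25 = (6.0 + 6.5)/25 = 0.50. A recurrence that is truly elsewhere belongs in neither the trial count nor the reference. The primary endpoint is exposed at two points only: the unbounded primary site, and the sentence on progressive disease in 12.1, which could be read as progression anywhere. The second reading would turn a separate brain deposit into a local failure, which moves the primary result in the opposite direction.

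**The case against.** The strongest reply is that the gap is narrow. Deaths count in progression-free survival, and deaths within a year count as failures on the primary endpoint. Spinal disease below the clavicles is distant. An eligible primary may already occupy brain or cavernous sinus, so an assessor could reasonably call contiguous recurrence there local. The sentence on progressive disease in 12.1 might capture more. The affected endpoints are descriptive, in 25 patients, with no hypothesis test. All of this stands and limits the size. It does not place a separate brain, dural, cranial leptomeningeal or skull recurrence anywhere.

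Four stronger readings are tempting, and the documents do not support them.

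- A reader might infer that the gap inflates the type 1 error. If the 50% is treated as an all-site failure rate and 4 points go uncounted, the probability of at most 8 failures in 25 rises from 0.054 to 0.114. The arithmetic is right, but the scenario is not this test, because the 50% is a local failure rate.
- A reader might infer that a patient with leptomeningeal recurrence and a stable tumour bed is wrongly a success on the primary endpoint. That recurrence is not local failure. Under correct definitions it is distant, and the patient, if alive and followed, remains local-failure-free.
- A reader might infer that nerve-tract recurrence is excluded from local failure. The text is ambiguous there because the primary site has no stated boundary.
- A reader might infer that Section 12.2 drops new nodes once other nodes have been irradiated. Its conditional sentence may only say how a treated node is judged, leaving the general nodal wording in force. Favourable bias in regional failure is not shown.

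**Conclusion.** Wrong as written. Sections 12.1 to 12.4 do not cover non-nodal recurrence above the clavicles that is not contiguous with the primary site. Such a recurrence is not a distant event, and it is not a progression event until death or a later classified event. Progression-free survival and distant-metastasis incidence are therefore biased favourably, by 4 points on a crude rate for each patient affected. How many patients that would be cannot be derived from the documents.

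The conclusion assumes that the progressive-disease sentence in 12.1 is read within its own section, as progression at the primary site. On the broader reading these recurrences would enter progression, but under the wrong site and into the primary endpoint. The text has to settle which reading holds. No effect on the type 1 error or power of the primary test is claimed.

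**What to change.** 1. **12.3:** remove the bracketed restriction and define distant failure as any recurrence that is neither local nor regional/nodal, naming non-contiguous brain, dural, leptomeningeal and skull disease.
2. **12.4:** state that recurrence at any site, or death, is a progression event.
3. **12.1:** limit progressive disease to the primary site and contiguous extension. State before analysis whether nerve-tract recurrence is local, consistently with how the historical 50% was counted. Making every recurrence in the nerve volume local is debatable: Section 9.2.2 draws that volume only for some histologies, so the primary endpoint would then differ by histology.
4. **12.2:** say that the treated-node sentence adds to, and does not replace, new nodal failure elsewhere.

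The cost is wording in four subsections and a site-of-recurrence field on the case report form. Progression-free survival and distant-metastasis results may be slightly less favourable. Capture remains limited to what clinical care or the scheduled scans detect. Table 4 lists MRI of the nasal cavity and sinuses with PET/CT at 3, 6, 12 and 24 months, and no dedicated brain imaging.
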